Table 2: Effect of TDF-based PrEP on estimated glomerular filtration rate in HIV-uninfected persons [Mugwanya et al. JAMA Int Med 2015]

	Net mean eGFR decline vs placebo (ml/min/1.73 ²)	
	Randomized TDF-based PrEP agent	
	FTC-TDF	TDF
Women	-1.73; p=0.02	-1.47; p=0.05

Figure 3. Contraceptive method selection by contracepting Ugandan women [Makerere University 2014]

Studies of bone turnover in DMPA users have suggested that the effects of DMPA on the skeleton are at least partially mediated through increased bone turnover, with increases in markers of bone resorption, N-terminal telopeptide of type I collagen (NTX), and bone formation, P1NP. In addition, DMPA reduces estradiol and sex hormone-binding globulin (SHBG) levels, resulting in hypoestrogenism that is often accompanied by amenorrhea and alters the balance of bone resorption and formation yielding impairments in bone mass.^{38, 52-56} Recent studies in animal

[figure not shown]
Table 3: Longitudinal studies of the association between DMPA and BMD loss

Study	Population	Anatomical site	Mean %Δ in BMD -
			DMPA vs Nonhormonal
Clark et al 2004	18-35 year old initiators	Hip	24 months: -5.7 vs <-0.4
		Lumbar spine	24 months: -5.7 vs <-0.4
Berenson et al 2004	18-33 year old initiators	Lumbar spine	24 months: -5.7 vs + 1.8
		Total hip	48 weeks: -1.6 vs 0.6; p<0.001
			240 weeks: -5.2 vs 0.2; p<0.001

models also suggest a role of estrogen to hasten recovery from kidney injury, leading to a hypothesis that subclinical kidney injury could be a consequence of hypoestrogenism.⁵⁷⁻⁵⁹

Thus, as TDF-based PrEP is delivered in settings where DMPA is commonly used, a large number of HIV-uninfected women will be exposed to two agents that are each known to reduce BMD. Their concurrent use may act additively or synergistically through pathways of subclinical kidney injury and/or hypoestrogenism to adversely affect bone health and the risk of future fracture (Figure 4).

Figure 4. Schematic of pathways through which concurrent TDF-based PrEP and DMPA use could impact bone density

Summary of the potential for joint effects of PrEP and DMPA on bone health

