We will use dual energy x-ray absorptiometry (DXA) scans to measure BMD annually at 3 anatomical sites (lumbar spine, total hip, and wrist). Additionally, we will derive the trabecular bone score (TBS), an index of lumbar spine trabecular microarchitecture.

Hypothesis: Relative to women using DMPA only (without tenofovir exposure) and women using PrEP only (without DMPA exposure), women concurrently using TDF-based PrEP and DMPA will have lower bone mass and more disruptions in bone microarchitecture.

2. We will investigate whether young women concurrently using TDF-based PrEP and DMPA experience: 1) higher rates of bone turnover, a direct precursor to bone loss and 2) subclinical kidney injury and hypoestrogenism, markers of two mechanistic pathways between TDF and DMPA use and bone mass

At baseline, 3, 6, 12, and 24 months, we will measure:

- 1) Markers of bone formation and resorption (e.g. NTX, P1NP, serum intact parathyroid hormone, total and bioavailable 25-OH-vitamin D)
- 2) Markers of kidney function (phosphate, glucose, creatinine, total protein, albumin) and
- 3) Markers of estrogen (serum estradiol, sex hormone binding protein, and the occurrence of amenorrhea)

Hypothesis: Relative to women using DMPA only and PrEP only, women concurrently using TDF-based PrEP and DMPA will have increased bone turnover markers and PTH. In addition, women concurrently using TDF-based PrEP and DMPA will have more frequent subclinical kidney injury (relative to women without tenofovir exposure) and reduced serum estrogen (relative to women without DMPA exposure).

3. Using mediation analysis, we will identify the degree to which the pathways through subclinical kidney injury and hypoestrogenism account for changes in bone density among women concurrently using TDF-based PrEP and DMPA

We will conduct mediation analysis to determine the degree to which changes in the pathways through subclinical kidney injury, hypoestrogenism and the combination of these pathways account for changes in bone density.

Hypothesis: The pathway through hypoestrogenism will be a stronger link between concurrent TDF-based PrEP and DMPA use and bone density changes.

Population

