- Current or recent history of primary or secondary amenorrhea
- Taking medications known to interfere with bone metabolism (steroids, anti-convulsants, bisphosphonates, cancer drugs).
- Has any other condition that would preclude the ability to provide informed consent, make study participation unsafe, complicate the interpretation of study findings or otherwise interfere with achievement of the study objectives, in the investigator's discretion.

Sample size and study power

Power calculations are based on the number of participants needed to achieve aim 1. Our target sample size is 500 women, of which 300 will be using DMPA and 200 will be using condoms for contraception. We calculate that with 300 women newly initiating DMPA and 75% of women choosing to initiate PrEP, thus with 225 women concurrently using PrEP and DMPA and 75 women using DMPA without PrEP, we will have >90% power to detect changes as low as 2.2% in BMD (with 1.0 g/cm² mean BMD loss) at any anatomical site between women using PrEP and DMPA concurrently and women using DMPA only during the 24 month follow up period (Table 4). Should more than 90% of women choose to initiate PrEP (270 women concurrently using PrEP and DMPA and 30 women using DMPA without PrEP), we will have 80% power to detect changes of >2.7% or more and should initiation rates be closer to 50% (150 women concurrently using DMPA and PrEP and 150 women using DMPA without PrEP), we will have >90% power for all comparisons.

Table 4. Power calculations. N=500: 300 on DMPA and 200 on condoms, shown with a range of PrEP acceptance for the primary comparison of DMPA + PrEP vs DMPA ($\alpha=0.05$)

Expected PrEP acceptance	Outcome: BMD (Aim 1)			Outcome: NTX (Aim 2)		
	Mean % Δ (std dev range)	Mean Δ	Power	Mean % Δ	Mean Δ	Power
75% (225 DMPA+PrEP, 75 DMPA)	2.2 (4–5) (0.5–1.0)	0.5 (0.5–1.0)	91%	2.2 (4–5)	0.10 (0.2 – 0.5)	>99%
75% (225 DMPA+PrEP, 75 DMPA)	2.5 (4–5) (0.5–1.0)	0.5 (0.5–1.0)	>96%	2.5 (4–5)	0.20 (0.2 – 0.5)	>96%
75% (225 DMPA+PrEP, 75 DMPA)	3 (4–5) (0.5–1.0)	1.0 (0.5–1.0)	>99%	3 (4–5)	0.50 (0.2 – 0.5)	>99%
90% (270 DMPA+PrEP, 30 PrEP)	2.5 (4–5) (0.5–1.0)	0.5 (0.5–1.0)	74-90%	2.5 (4–5)	0.10 (0.2 – 0.5)	>99%

Recruitment

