The primary analysis will be separate comparisons of the annualized rates of change in BMD and TBS of the spine and hip between women using PrEP and DMPA concurrently versus women using DMPA only (comparison 1), women using PrEP only (comparison 2), and women using neither (comparison 3). Analyses will account for baseline BMD.

Aim 2, part 1. We will investigate whether young women concurrently using TDF-based PrEP and DMPA experience higher rates of bone turnover relative to women using either agent singly or neither agent

This outcome will be defined by the percent change from baseline of serum levels of NTX and P1NP over 24 months. Secondary outcomes will include: 1) percent change from baseline in serum levels of intact PTH, total 25-(OH)D, bioavailable (i.e. unbound or free) 25-(OH)D calculated from vitamin D binding protein (VDBP) using the standard equation.

$$\text{Free 25(OH)D} = \frac{\text{total 25(OH)D}}{1 + (6 \times 10^3 \times \text{albumin}) + (7 \times 10^8 \times \text{DBP})}$$

To test the hypothesis that combined PrEP and DMPA use is associated with greater bone turnover than DMPA use alone, we will use time-dependent linear mixed-effects regression models to compare mean percent changes in NTX and P1NP between concurrent users of PrEP and DMPA versus users of DMPA only. Secondary powered comparisons will be between: a) concurrent users of PrEP and DMPA versus users of PrEP only; b) users of PrEP only versus users of condoms only; c) users of DMPA only vs users of condoms only. Analysis of the percent change from baseline in serum levels of intact PTH, total 25-OH-D and bioavailable 25-OH-D over 24 months will follow a similar approach. All analyses will be adjusted for confounders and we will consider a broad range of demographic, medical, lifestyle, and sexual behavior characteristics as potential confounders.

Aim 2, part 2. We will investigate whether young women concurrently using TDF-based PrEP and DMPA experience elevated markers of subclinical kidney injury relative to women using TDF-based PrEP alone

This outcome will be defined as having either:

- 1) eGFR decline ($\geq 25\%$ decline from baseline or creatinine clearance $< 60 \text{ mL/min}$). GFR will be calculated using the Chronic Kidney Disease Epidemiology (CKDE) collaboration equation

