- 2) proximal tubular injury (tubular proteinuria defined as elevated urine protein with urine albumin-protein ratio < 0.4 , euglycemic glycosuria, phosphaturia defined as increased urinary excretion of phosphorus $> 15\%$ or maximum rate of tubular phosphate reabsorption to the glomerular filtration rate).

These markers were selected because they are routinely available in clinical practice and have been used in prior studies. The cutoff of $\geq 25\%$ for eGFR decline was adapted from established criteria for the diagnosis of acute kidney injury;⁴¹ eGFR decline of this magnitude has been associated with increased morbidity and mortality.²²⁻²⁴

To determine whether young women using PrEP alone or concurrently with DMPA experience higher rates of subclinical kidney injury, we will perform a qualitative comparison of the incidence of individual markers of kidney injury among women using PrEP (alone or concurrently with DMPA) versus women who have no exposure to TDF.

Aim 2, part 3. We will investigate whether young women concurrently using TDF-based PrEP and DMPA experience elevated markers of hypoestrogenism relative to women using DMPA alone

This outcome will be defined as the percent change from baseline serum estradiol over 24 months and we will adjust for sex hormone-binding protein.⁵⁶ The secondary outcome will be based on self-reported missed menses, with > 3 missed menses in a row categorized as amenorrhea.

To determine whether young women concurrently using DMPA alone or concurrently with PrEP experience greater frequency of hypoestrogenism, we will conduct time-dependent logistic

regression among women using DMPA and women not exposed to DMPA, comparing the proportion of visits with hypoestrogenism.

Aim 3. Using mediation analysis, we will identify the degree to which the pathways through subclinical kidney injury and hypoestrogenism account for changes in bone density among women concurrently using TDF-based PrEP and DMPA

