For clinical data collection, standardized surveys will be used that will include questions on sensitive topics, such as sexual behavior. All participants will be extensively counseled about the risk for HIV transmission with sex unprotected by a condom and/or PrEP and the importance of using condoms consistently and correctly. We expect that the risk of HIV transmission will actually be lower in the proposed novel cohort than the general population of young women due to the careful attention that will be given to counseling women about HIV risk and the provision of PrEP. Study staff will be aware of the potential for confidentiality issues with regards to test results from HIV testing that are part of a participant's study documents. For minors who enroll with parental consent, results of HIV testing will be confidential and not available to the parent or guardian. But the study will stipulate that minors will be encouraged to disclose positive results to a responsible adult, which need not be their legal guardian. Support will be provided for such disclosures.

There is the potential for confidentiality issues with regards to study data. Particularly, since parental consent will be required for some participants under the age of 18, these participants would have to share their choice to participate in a study that will follow their contraceptive and PrEP use choices and collect detailed sexual behavior data, whereas otherwise they may not have chosen to disclose this information. Should there be any psychosocial stress associated with participation in the study, counseling by study staff will be provided, or referral to appropriate mental health professionals will be done. The age of consensual sex is 16 years, and therefore underage sex is not an issue in this protocol.

Benefits

Participants will receive individualized HIV risk-reduction counseling and counseling about pregnancy planning and prevention of unintended pregnancy, access to PrEP medication, contraceptives, and free condoms. In addition, participants may benefit in the future from information learned from this study.

Care for persons identified as HIV positive

Women who become infected with HIV will be referred immediately to HIV care centers and encouraged to initiate antiretrovirals in line with Ugandan national antiretroviral guidelines.

Seroconverters who become pregnant will be referred for prevention of mother to child HIV transmission services.

Treatment for injury

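### The Aim 2 kidney comparison puts PrEP+DMPA and PrEP-only women on the same side, so it cannot answer its own heading, and its crude PrEP contrast is open to confounding by DMPA

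*Protocol*

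**What the plan says.** The heading of Aim 2 part 2 (protocol, section V) says the study will find out whether concurrent users "experience elevated markers of subclinical kidney injury relative to women using TDF-based PrEP alone". The analysis paragraph under that heading sets out something else. Its method is put this way: "we will perform a qualitative comparison of the incidence of individual markers of kidney injury". The two sides to be set against each other are then defined as "among women using PrEP (alone or concurrently with DMPA) versus women who have no exposure to TDF". One side is therefore PrEP+DMPA plus PrEP only, and the other is DMPA only plus neither agent. No model, stratification or adjustment is named for this comparison.

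The Aims in section III give a third version, in which "women concurrently using TDF-based PrEP and DMPA will have more frequent subclinical kidney injury (relative to women without tenofovir exposure"). There the index group is concurrent users only.

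Three other statements bear on the point:
- Section II, on DMPA and bone metabolism, cites animal work on estrogen and recovery from kidney injury, "leading to a hypothesis that subclinical kidney injury could be a consequence of hypoestrogenism". The same paragraph says that DMPA produces hypoestrogenism.
- Section III, Overall Design, has PrEP offered to every woman. It is not assigned.
- Section III, Sample size: "Our target sample size is 500 women, of which 300 will be using DMPA and 200 will be using condoms for contraception". PrEP uptake is projected at 75%, 90% or 50%, in each case among the 300 DMPA women.

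**The concern.** There are two separate problems.

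The first is a mismatch between question and comparison. The effect of adding DMPA to PrEP can be seen only by setting PrEP+DMPA against PrEP only. The analysis paragraph merges those groups, so any difference between them disappears into an average.

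The second is confounding of the contrast that is made. Women choose PrEP, and nothing in the design makes uptake equal in DMPA and condom users. If uptake differs, the share of DMPA users differs between the two pooled sides. If DMPA also changes kidney markers, which is the possibility the part 2 heading sets out to examine, then part of the PrEP versus no-TDF difference is a DMPA difference. It could look like TDF kidney toxicity or hide it. The study's stated primary objective is the safety of concurrent use, so the reading of this table matters even though the kidney outcome is not the one on which the study is sized.

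**Working it through.** **Check of the group sizes.** The protocol gives no power or sample size for the kidney outcome. Its group sizes can be checked against the BMD row of Table 4: 225 versus 75 women, difference 2.2%, SD 5, two-sided alpha 0.05.
- SE = 5 × √(1/225 + 1/75) = 0.667
- 2.2/0.667 = 3.30
- power = Φ(3.30 − 1.96) = 0.910, against the stated 91%

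**Question against comparison.**

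| Place | Index group | Comparator |
|---|---|---|
| Part 2 heading | PrEP+DMPA | PrEP only |
| Aims, hypothesis 2 | PrEP+DMPA | no tenofovir |
| Part 2 analysis paragraph | PrEP+DMPA and PrEP only | DMPA only and neither |

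The third row contains no contrast between PrEP+DMPA and PrEP only. This holds whatever the uptake.

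**Size of the confounding.** Inputs from the protocol: 300 DMPA and 200 condom women. Assumed, because the protocol does not give them: PrEP uptake in condom users; a DMPA risk ratio r = 2 for a kidney marker; no PrEP effect; marker risk 5% without DMPA and so 10% with it. An uptake of 85% among DMPA users is also an assumption, whereas 50%, 75% and 90% are the protocol's scenarios for that group.

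Let s₁ be the DMPA share among PrEP users and s₀ the share among women without TDF. Then

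pooled ratio = [1 + s₁(r − 1)] / [1 + s₀(r − 1)]

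The 5% base risk cancels.

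| Uptake DMPA/condom | PrEP side: DMPA + condom | No-TDF side: DMPA + condom | s₁ vs s₀ | Expected events | Pooled ratio |
|---|---|---|---|---|---|
| 75%/75% | 225+150 | 75+50 | 60.0% vs 60.0% | 30/375 vs 10/125 | 1.00 |
| 75%/50% | 225+100 | 75+100 | 69.2% vs 42.9% | 27.5/325 vs 12.5/175 | 1.18 |
| 85%/65% | 255+130 | 45+70 | 66.2% vs 39.1% | 32/385 vs 8/115 | 1.19 |
| 75%/90% | 225+180 | 75+20 | 55.6% vs 78.9% | 31.5/405 vs 8.5/95 | 0.87 |
| 90%/50% | 270+100 | 30+100 | 73.0% vs 23.1% | 32/370 vs 8/130 | 1.41 |
| 50%/90% | 150+180 | 150+20 | 45.5% vs 88.2% | 24/330 vs 16/170 | 0.77 |

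Within each contraceptive method the ratio is 1.00 in every row.

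**Sensitivity.**
- r = 1.5: the pooled ratio is 1.11 at 75%/50%, 0.92 at 75%/90%, 1.22 at 90%/50% and 0.85 at 50%/90%.
- r = 1: it is 1.00 at any uptake.
- True PrEP ratio 1.50 with r = 2: the pooled figure reads 1.78, 1.30, 2.11 and 1.16 in the same four cases. The within-method ratio stays at 1.50.

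**Precision of the alternative.** For each two-group ratio, SE of the log ratio = √(1/a − 1/n₁ + 1/c − 1/n₀), with a and c the events among n₁ and n₀ women. For the Mantel-Haenszel ratio the standard Greenland-Robins variance is used. With r = 2:
- 75%/75%: crude 0.35. DMPA stratum (22.5/225 vs 7.5/75) 0.40. Condom stratum (7.5/150 vs 2.5/50) 0.71. Mantel-Haenszel 0.35.
- 90%/50%: crude 0.38; Mantel-Haenszel 0.42.

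**The case against.** The strongest case on the other side has four parts.

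*The bias is conditional.* It needs a DMPA effect on the kidney and unequal uptake, and the protocol gives no figure for either. The kidney hypothesis for estrogen rests on animal work. The protocol mainly presents kidney injury as a TDF effect and describes the two agents as acting through separate pathways, so pooling over DMPA has some logic. This stands, and it is why the size can be given only as a range under assumptions. It does not touch the mismatch with the heading.

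*The comparison is descriptive.* At 90%/50%, 32/370 versus 8/130 gives SE 0.382 and a 95% interval of 1.41 × exp(±1.96 × 0.382), about 0.66 to 2.97, so the bias lies inside sampling error. That is true under these assumptions. But sampling error does not cancel a systematic shift, and a qualitative reading has no interval to warn the reader.

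*Adjustment is promised.* A sentence says that all analyses will be adjusted for confounders. It stands at the end of Aim 2 part 1, after the mixed models, and lists demographic, medical, lifestyle and sexual behaviour characteristics without naming DMPA. Part 2 states no model in which adjustment could be made.

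*Layout belongs in a SAP.* A SAP could add tables by group. Here, however, the protocol itself has fixed which groups are compared.

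A reader might also infer more than the document supports:
- That the bias passes into Aim 3. It does not follow, because the Aim 3 models condition on both TDF and DMPA exposure and do not take the pooled contrast as an input.
- That Aim 2 part 3 has the mirror fault, since it plans "regression among women using DMPA and women not exposed to DMPA, comparing the proportion of visits with hypoestrogenism". That would need PrEP to affect estrogen or menses; no mechanism is stated, and a regression leaves room for adjustment.
- That condom users will decline PrEP because the Risks section speaks of "risk for HIV transmission with sex unprotected by a condom and/or PrEP". This is counselling text, and and/or includes using both.
- That the sample size section contemplates 90% uptake in one group with 50% in the other. Its scenarios are alternatives for DMPA users only.

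**Conclusion.** The point holds in two parts of different strength. The mismatch is unconditional: the comparison in Aim 2 part 2 cannot answer the question in its heading. The confounding is conditional on DMPA affecting kidney markers and on PrEP uptake differing by contraceptive method. With an assumed DMPA risk ratio of 2 and no PrEP effect, moderate differences in uptake shift the pooled ratio to between 0.87 and 1.19. The values 1.41 and 0.77 join opposite extremes of uptake and should be read as outer cases. With equal uptake or no DMPA effect there is no bias. This is a worthwhile, inexpensive correction to a secondary comparison and leaves the primary BMD analysis untouched.

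**What to change.** Replace the analysis sentence of Aim 2 part 2 with the following plan:
1. Report the incidence of each kidney marker in all four exposure groups: PrEP+DMPA, PrEP only, DMPA only, neither.
2. For the question in the heading, compare PrEP+DMPA with PrEP only.
3. For the PrEP effect, compare within contraceptive method: PrEP+DMPA with DMPA only, and PrEP only with neither. If one overall figure is wanted, combine the two strata by a Mantel-Haenszel risk ratio or risk difference.

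This matches the separate group comparisons already planned for Aim 1 and Aim 2 part 1. It needs no new data or visits.

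The cost is precision. The combined estimate is at most slightly less precise than the crude one: no visible loss at 75%/75%, and an SE of 0.42 against 0.38 at 90%/50%. The single-stratum estimates are clearly less precise. Among condom users at 75% uptake, with only 2.5 expected events among the 50 women using neither agent, the SE is about twice the crude value (0.71 against 0.35), and that stratum should be presented with this caution.

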Our goal for this analysis is to assess the relative magnitude of each pathway on BMD. To define each mediator pathway, we will use the set of markers that is most predictive of the mean percent change in BMD. For the subclinical kidney injury pathway, the set of markers may include phosphate, glucose, creatinine, total protein, and albumin. Because the relationship between TDF-induced subclinical kidney injury and dysregulation of PTH and vitamin D metabolism remains unclear, we will also consider bioavailable 25-OH vitamin D, and/or intact PTH measurements as potential markers of this pathway. In secondary analyses, we will consider markers of bone turnover as an alternative outcome to BMD changes. For the hypoestrogenism pathway, the set of markers may include estradiol, sex hormone-binding globulin, and/or amenorrhea.

We will estimate the crude and adjusted direct and indirect effects of concurrent TDF-based PrEP and DMPA use on mean percentage change in BMD through each pathway by constructing separate regression models of BMD conditional on TDF and DMPA exposure, the mediator's occurrence, and baseline covariates. We will compute the proportion mediated by each mediator individually as well as the both mediators concurrently closed form estimators. Bootstrapping will be used to compute standard errors. Our interpretation of these results will carefully specify model assumptions including no unmeasured confounding between the exposure and outcome, exposure and mediators, and mediators and outcome.⁶³

VI. HUMAN SUBJECTS CONSIDERATIONS

The protocol, informed consent forms (for cohort participation and for interviews of providers), and patient education and recruitment materials will be reviewed and approved by the IRBs/ECs responsible for oversight. Subsequent to initial review and approval, the responsible IRBs/ECs will review the study at least annually.

Study oversight

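### Aim 3 compares two mediating pathways using one-mediator models and markers chosen on the outcome, so individual shares can overlap if the pathways are linked

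*Protocol*

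**What the plan says.** The protocol's Data Analysis section for Aim 3 states its purpose directly: "Our goal for this analysis is to assess the relative magnitude of each pathway on BMD". The Aims section adds a directional hypothesis: "The pathway through hypoestrogenism will be a stronger link between concurrent TDF-based PrEP and DMPA use and bone density changes".

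The method has four parts that matter here.

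- **Markers.** For each mediator pathway, "we will use the set of markers that is most predictive of the mean percent change in BMD". Seven candidates are named for kidney (five core markers, plus bioavailable 25-OH vitamin D and PTH) and three for hypoestrogenism.
- **Models.** Direct and indirect effects are obtained "by constructing separate regression models of BMD conditional on TDF and DMPA exposure", the occurrence of the mediator (in the singular) and baseline covariates. I read this as one mediator per model.
- **Shares.** "We will compute the proportion mediated by each mediator individually as well as the both mediators concurrently".
- **Precision.** "Bootstrapping will be used to compute standard errors". The text does not say whether marker selection is repeated in each resample.

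The Background (Effects of DMPA on bone metabolism) cites animal work, where "models also suggest a role of estrogen to hasten recovery from kidney injury". It then takes this one step further, "leading to a hypothesis that subclinical kidney injury could be a consequence of hypoestrogenism". No order between the two mediators is stated in Aim 3.

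**The concern.** Two features of the plan bear on the comparison of pathways.

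**Separate models.** Suppose hypoestrogenism does contribute to kidney injury. Estrogen is then a common cause of the kidney mediator and of BMD, and is itself moved by exposure. A kidney-only model omits it. That model credits kidney with part of estrogen's effect, and it breaks the plan's own assumption of no confounding between mediator and outcome. The path from estrogen through kidney to BMD is also counted in both individual shares. The planned two-mediator estimate protects the combined share. The protocol does not say that the comparison comes from that model, and without an order even that model cannot say which pathway owns the shared path.

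**Selection on the outcome.** Markers are chosen because they predict BMD change, and the same women and the same outcome then supply the mediated share. Chance association is built into the choice.

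At stake are the relative magnitude that Aim 3 sets out to report and, under some conditions, the ranking that it hypothesises.

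**Working it through.** The protocol gives no sample size, power or error figure for Aim 3, so there is none to reproduce. Every effect size below is an assumption.

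**1. Inputs.** From the sample size section: 225 concurrent users and 75 DMPA-only users among 300, and 200 condom users. Assumed: 75% PrEP uptake among condom users too, giving 150 and 50. Simulations used 275 women (225 concurrent, 50 neither) or all 500.

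**2. Overlap, worked by hand.** Let exposure shift estrogen by 0.5 SD and kidney by a further 0.5 SD of its own. Let c be the estrogen-to-kidney coefficient, with unit residual variances, a linear model, no interaction and a total effect of 1.0. Take BMD coefficients of 0.4 (kidney) and 0.6 (estrogen). Kidney's own share is 0.4 × 0.5 = 20% and estrogen's direct share is 0.6 × 0.5 = 30%.

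- Kidney-only share = [0.4 + 0.6c/(1+c²)] × (0.5 + 0.5c)
- Estrogen-only share = (0.6 + 0.4c) × 0.5
- True combined share = 0.4 × (0.5 + 0.5c) + 0.6 × 0.5

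At c = 0.5 the kidney-only share is (0.4 + 0.24) × 0.75 = 48%, the estrogen-only share is 0.8 × 0.5 = 40%, and the combined share is 0.30 + 0.30 = 60%.

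| c | Kidney-only | Estrogen-only | Sum | True combined | Joint, no order (kidney / estrogen) | Joint, estrogen first (kidney / estrogen) |
|---|---|---|---|---|---|---|
| 0 | 20% | 30% | 50% | 50% | 20 / 30% | 20 / 30% |
| 0.1 | 25% | 32% | 57% | 52% | 22 / 30% | 20 / 32% |
| 0.3 | 37% | 36% | 73% | 56% | 26 / 30% | 20 / 36% |
| 0.5 | 48% | 40% | 88% | 60% | 30 / 30% | 20 / 40% |

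The 48% splits into 20 points of kidney's own effect, 10 points of the shared path (0.4 × 0.25) and 18 points of estrogen's direct effect (0.24 × 0.75).

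In simulated samples of 275 or 500 women, the separate models rank kidney first in 27-29%, 50-53% and 73-76% of runs at c = 0.1, 0.3 and 0.5. The ordered joint model does so in 14-17%, 9-12% and 7-10%. At c = 0 the separate models already do so in 19-22%, from sampling noise alone.

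**3. Kidney with no effect on BMD.** The kidney-only share equals the estrogen share × c(r+c)/(1+c²), where r is exposure's own shift in kidney divided by its shift in estrogen. With r = 1 and an estrogen share of 30-50%, it is 3-5%, 11-18% and 18-30% at c = 0.1, 0.3 and 0.5; the joint model gives 0%. Kidney overtakes estrogen only if r > 1/c, that is 3.3 at c = 0.3 or 2 at c = 0.5.

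A second simulation (500 women, true kidney share 0, estrogen share about 35%) agrees. At mediator correlations of 0.3 and 0.5 the kidney-only share is 5% and 9% if only TDF moves kidney, and 10% and 17% if DMPA moves it too. At zero correlation it is 0%, and the joint model gives 0% throughout.

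**4. Selection, no mediation.** Exposure is in the selection model and selection is not repeated in the bootstrap. Paired values are 275 / 500 women.

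| Selection | Bootstrap SE / true SD | 95% percentile coverage | Coverage, selection repeated |
|---|---|---|---|
| Kidney, best set | 0.79 / 0.77 | 83.7 / 83.4% | 97.8 / 97.9% |
| Kidney, single best | 0.64 / 0.63 | 73.2 / 72.2% | 97.2 / 97.2% |
| Estrogen, best set | 0.79 / 0.80 | 87.5 / 87.6% | 95.8 / 96.1% |
| Estrogen, single best | 0.75 / 0.75 | 85.8 / 85.2% | 95.8 / 95.5% |

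One fixed marker gives a ratio of 1.02-1.06 and coverage of 94-95%. Intervals built as estimate ± 1.96 SE do better after selection, at 90-96%. A repeat of the single-best case gave coverage of 70-86%. A setting with other effect sizes gave 80% (best of 3) and 65% (best of 7).

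If markers are ranked without exposure in the model, false shares of 1.5-3.5% arise, and repeating the selection leaves coverage at 75-91%.

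**5. Selection, real mediation.** With 10-30% mediated, the SE ratio is 0.83-0.97 for the best set and 0.91-1.20 for a single best marker. The estimate now tends upward: 10-20% above a fixed marker in one setting. In another, with a true effect of -0.20 per marker, it averaged -0.36 (best of 3) and -0.48 (best of 7). That excess is over the effect of one marker, not over the whole pathway. There, repeating the selection lowered coverage from 91.5% to 81% and from 77% to 56%.

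**The case against.** The strongest reply is that the protocol already plans the two-mediator estimate and cites a methods paper on mediation with several mediators. Bootstrap mechanics and mediator order are also commonly left to a statistical analysis plan, which is not shown here. This stands in part. The combined share is protected, and silence on the bootstrap is not an error in itself. But the outcome-driven marker rule and the separate models are fixed in the protocol, and nothing ties the comparison to the joint model.

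The link between mediators is only a hypothesis from animal work. The Background summary of joint effects describes separate pathways for the two agents and treats cross-pathway effects as unknown. This stands: the overlap is conditional.

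The plan speaks of the mediator's occurrence and Table 5 defines kidney injury by thresholds, whereas the working uses continuous mediators and, in the overlap part, no measurement error. The sizes are therefore illustrative.

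Fixing one marker is no cure either. With a 20% pathway share and markers that are half signal, a fixed marker showed 10% and a selected one 11-12%. This stands, and it argues for a prespecified set.

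Three stronger readings go beyond the documents:

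- **Errors are understated in general.** That is a no-mediation result, and it needs a bootstrap that holds the selection fixed, which the protocol does not say.
- **The ranking will reverse.** That needs particular shares and a sizeable link.
- **The longer kidney list favours kidney.** No direction follows, because it depends on marker quality, which the protocol does not give.

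**Conclusion.** The point holds in a conditional form and should be fixed, though it is not critical to the trial. If the mediators are linked as the Background hypothesises, the one-at-a-time shares overlap and the kidney share is too large. Under the assumed 20%/30% split the excess over kidney's own effect is 5, 17 and 28 percentage points at c = 0.1, 0.3 and 0.5, enough to put kidney level with or ahead of estrogen at the two larger values. With no link this excess is zero.

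Selecting markers on the outcome adds a second, smaller weakness: poor percentile coverage when there is no mediation and the selection is held fixed, and an upward tendency when mediation is real. In the latter case standard errors are roughly right or only mildly too small.

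The overlap does not touch the combined share, and Aims 1 and 2 are unaffected. The mechanism follows from the protocol's text; the sizes rest on assumed effects. Confidence is medium.

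**What to change.** - Take the pathway comparison from the already planned model with both mediators.
- State the mediator order, for example estrogen before kidney as the Background suggests, with the reverse order and no order as sensitivity analyses.
- Report the one-at-a-time proportions as secondary, with a note that they can overlap and need not add up to the combined share.
- Fix each pathway's marker set in advance on biological grounds. A set is preferable to a single marker, which may capture only part of its pathway.
- If data-driven selection is kept as a sensitivity analysis, keep exposure in the selection model and cross-fit it, selecting and estimating on separate folds. Repeating the selection in the bootstrap alone restores coverage under no mediation but does not remove selection bias.

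The cost is wording and modest programming, with no new data. Reported shares may be smaller and intervals wider. The stated order is an assumption that the data cannot confirm, so the sensitivity analyses belong beside the main result.
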